7.6 Safety

For all safety related analyses, refer to the Core Safety SAP⁶. Safety will be summarized for: all treated subjects by treatment group as treated.

7.6.1 Deaths

See Core Safety SAP⁶.

7.6.2 Serious Adverse Events

See Core Safety SAP⁶.

7.6.3 Adverse Events Leading to Discontinuation of Study Therapy

See Core Safety SAP⁶.

7.6.4 Adverse Events Leading to Dose Delay of Study Therapy

See Core Safety SAP⁶.

7.6.5 Adverse Events

See Core Safety SAP⁶.

7.6.7 Immune-Mediated Adverse Events

See Core Safety SAP⁶.

7.6.8 Immune Modulating Medication

See Core Safety SAP⁶.

7.6.9 Multiple Events

See Core Safety SAP⁶.

7.6.10 Clinical Laboratory Evaluations

The analysis population for each laboratory test is restricted to treated subjects who underwent that laboratory test.

7.6.10.1 Hematology

See Core Safety SAP⁶.

7.6.10.2 Serum Chemistry

[figure not shown]
See Core Safety SAP⁶.

[figure not shown]
7.6.12 Vital Signs and Pulse Oximetry

[figure not shown]
See Core Safety SAP⁶.

[figure not shown]
7.7 Pregnancy

[figure not shown]
See Core Safety SAP⁶.

[figure not shown]

7.13 End of Study Analyses at Study Closure

Subjects who have continued on study treatment following the study unblinding will be followed per protocol through treatment discontinuation and safety follow-up.

The end of study analyses will be performed for the selected safety data and duration of treatment using all randomized subjects.

Data to be reported:

- Subject disposition
- Duration of treatment (Nivolumab, Temozolomide)
- Death
- Adverse events
- Serious adverse events

8 CONVENTIONS

The following conventions may be used for imputing partial dates for analyses requiring dates:

For missing and partial adverse event onset dates, imputation will be performed using the Adverse Event Domain Requirements Specification⁹. Missing and partial Non-Study Medication Domain dates will be imputed using the derivation algorithm described in 4.3.3 of BMS Non-Study Medication Domain Requirements Specification¹⁰.

For death dates, the following conventions will be used for imputing partial dates:

- If only the day of the month is missing, the 1st of the month will be used to replace the missing day. The imputed date will be compared to the last known date alive day and the maximum will be considered as the death date.
- If the month or the year is missing, the death date will be imputed as the last known date alive day
- If the date is completely missing but the reason for death is present the death date will be imputed as the last known date alive day

For date of progression, the following conventions will be used for imputing partial dates:

- If only the day of the month is missing, the 1st of the month will be used to replace the missing day*.
- If the day and month are missing or a date is completely missing, it will be considered as missing.

*In cases where the date of death is present and complete, the imputed progression date will be compared to the date of death. The minimum of the imputed progression date and date of death will be considered as the date of progression.

For other partial/missing dates, the following conventions may be used:

- If only the day of the month is missing, the 15th of the month will be used to replace the missing day.
- If both the day and the month are missing, “July 1” will be used to replace the missing information.
- If a date is completely missing, it will be considered as missing.

The following conversion factors will be used to convert days to months or years: 1 month = 30.4375 days and 1 year = 365.25 days.

Duration (e.g. time from first diagnosis to first dosing date, duration of response, and time to response) will be calculated as follows:

$$\text{Duration} = (\text{Last date} - \text{first date} + 1)$$

All statistical analyses will be carried out using SAS (Statistical Analysis System software, SAS Institute, North Carolina, USA) unless otherwise noted.

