#### **3.6.2 Lost to Follow-Up**

All reasonable efforts must be made to locate subjects to determine and report their ongoing status. This includes follow-up with persons authorized by the subject as noted above. Lost to follow-up is defined by the inability to reach the subject after a minimum of three documented phone calls,

faxes, or emails as well as lack of response by subject to one registered mail letter. All attempts should be documented in the subject's medical records. If it is determined that the subject has died, the site will use permissible local methods to obtain the date and cause of death.

If investigator's use of third-party representative to assist in the follow-up portion of the study has been included in the subject's informed consent, then the investigator may use a Sponsor-retained third-party representative to assist site staff with obtaining subject's contact information or other public vital status data necessary to complete the follow-up portion of the study. The site staff and representative will consult publicly available sources, such as public health registries and databases, in order to obtain updated contact information. If after all attempts, the subject remains lost to follow-up, then the last known alive date as determined by the investigator should be reported and documented in the subject's medical records.

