- For this study, tumor scan measurements are reviewed by blinded independent radiologic review (BICR) in a batch read mode, i.e., independent reviews commence after all exams for each time point have been received. It is challenging to obtain data in real time. Due to delayed BICR data, the number of PFS events passed the pre-specified events required for interim analysis and it was close to the number of pre-specified PFS events required for final analysis. As a result, interim analysis for PFS will not be conducted.
- The Data Monitoring Committee (DMC) reviewed all available data on 09-Dec-2020 and agreed that there is no plausible scenario for this study to have a positive OS result at the final analysis based on either all randomized patients or on patients without baseline corticosteroids. This statement is based on the DMC's review of the OS results to date, with over 80% of the final required number of events reached and related statistical considerations including conditional power (CP) of < 1% for a statistically significant final result. Therefore, the DMC recommended to unblind the sites and patients, which was approved by the sponsor. The study was officially unblinded on 22-Dec-2020.

As a consequence, the timing of the primary OS analysis, originally planned when 337 and 494 events were to be reached respectively for the population without corticosteroid at baseline and the overall population, has been updated. It is no longer event-driven.

To prevent any bias due to unblinding of patients, the primary OS analysis and the safety analysis will be conducted using the cut-off date of 22-Dec-2020, which is when the study was unblinded. The primary analysis of PFS per BICR will be conducted using the cut-off date of 14-Jun-2019 with a database lock date of 09-Aug-2019 (the primary PFS analysis assessed by

the DMC in 2019). The same analysis will also be conducted using the cut-off date of 22-Dec-2020.

- The efficacy analyses will be performed for the primary and secondary endpoints. All the secondary endpoints will be analyzed at the same time as the primary endpoints using the analysis methods already defined in the current SAP.

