If the hypothesis cannot be rejected, then the study continues to proceed to the OS analysis. If, however, the hypothesis can be rejected, graph will be updated as per Algorithm 1 of Maurer and Bretz (2013), the algorithm ensures that in case PFS in the first 558 subjects from all randomized population is rejected, its entire alpha level (i.e., 0.01) is passed to OS in all randomized subjects without baseline corticosteroids. A simple hypothetical example is illustrated in Figure 7.5.4-2 and Figure 7.5.4-3.

Figure 7.5.4-2: Rejection of PFS in the First 558 Subjects from All Randomized Population

[figure not shown]

* first 558 subjects from all randomized population

** Nominal significance levels for based on O'Brien-Fleming with 70% observed information fraction

Further, if OS in all randomized subjects with no baseline corticosteroid is rejected, its significance level is passed to the OS in all randomizes subjects (see Figure 7.5.4-3).

Figure 7.5.4-3: Rejection of OS in All Randomized Population without Baseline Corticosteroids

** Nominal significance levels for based on O’Brien-Fleming with 70% observed information fraction

*** Nominal significance levels based on Pocock with 70% observed information fraction

Each time a hypothesis is rejected and the graph is updated, the alpha levels for IA and FA will be recalculated for each remaining OS endpoint using Lan-DeMets alpha spending function (O’Brien-Fleming boundaries will be used for OS in all randomized subjects without baseline corticosteroids, and Pocock boundaries will be used for OS in all randomized subjects). At the time of the final OS analysis, all events in the database at the time of the lock will be used.

Secondary endpoints are not included in a hierarchy of testing and, thus, these comparisons are not adjusted for multiplicity across endpoints. Analyses of the secondary OS and PFS endpoints (including p-values) will be performed for descriptive purpose only.

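### A death date with a known year but no month is set to the last known alive date, so the imputed death can fall in a year that the record itself rules out

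*SAP*

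**What the plan says.** SAP Section 8 (Conventions) has three rules for incomplete death dates.

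- Only the day is missing: the first of the known month is imputed, and then "The imputed date will be compared to the last known date alive day and the maximum will be considered as the death date".
- More than the day is absent, so that either of the other two parts was not recorded. Here the SAP's instruction reads: "If the month or the year is missing, the death date will be imputed as the last known date alive day".
- The date is wholly missing but a reason for death is given: the last known alive date is used.

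The section treats a known year differently for other dates. For the residual class of dates, the rule that begins "If both the day and the month are missing" imputes 1 July of the recorded year. A progression date with only a year is treated as missing. The section opens permissively ("The following conventions may be used for imputing partial dates for analyses requiring dates"), but the death-date rules themselves are worded as what will be done.

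Under Changes to the Planned Analyses, the SAP states that "the primary OS analysis and the safety analysis will be conducted using the cut-off date of 22-Dec-2020", and gives avoidance of bias from unblinding as the reason. SAP 7.5.4 adds: "At the time of the final OS analysis, all events in the database at the time of the lock will be used". Neither place says whether the cut-off is compared with recorded or imputed dates.

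**The concern.** When only the day is missing, the SAP keeps what is known: the imputed death cannot fall before the recorded month or before the last known alive date. When the month is also missing, the recorded year is dropped. If the last contact was in an earlier year, the rule gives a death date on which the subject is known to have been alive. Each such OS time is too short, and so is PFS when death is the event.

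The cut-off raises a second question. It was chosen to keep information from after unblinding out of the primary OS analysis. If dates are imputed before the cut is applied, a death known to have happened in 2021 could be moved back to a last-alive date in 2020 and counted as an event.

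**Working it through.** The plan states no figure for this point, so there is none to reproduce. The check applies the rule to example records and then puts a scale on the result.

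**Inputs.** Death-date rules: SAP Section 8. Cut-off of 22-Dec-2020: SAP Changes to the Planned Analyses. Survival contact every 3 months until unblinding: Protocol Table 5.1-3. Over 80% of the 337 and 494 planned events reached at the monitoring committee's review: Protocol 8.4.2.1.

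**Rules compared, for a known year and missing month.**
- SAP: D = L, where L is the last known alive date.
- Year floor: D = max(L, 1 January of the recorded year).

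| L | Death recorded as | SAP date | Floored date | Difference (days) | On or before cut-off: SAP / floor |
|---|---|---|---|---|---|
| 10-Oct-2018 | 2019 | 10-Oct-2018 | 01-Jan-2019 | 83 | yes / yes |
| 15-Nov-2019 | 2020 | 15-Nov-2019 | 01-Jan-2020 | 47 | yes / yes |
| 15-Mar-2020 | 2020 | 15-Mar-2020 | 15-Mar-2020 | 0 | yes / yes |
| 15-Nov-2020 | 2021 | 15-Nov-2020 | 01-Jan-2021 | 47 | yes / no |
| 22-Dec-2020 | 2021 | 22-Dec-2020 | 01-Jan-2021 | 10 | yes / no |
| 20-Jan-2021 | 2021 | 20-Jan-2021 | 20-Jan-2021 | 0 | no / no |

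For the top row, the days from 10 October to 1 January are 21 + 30 + 31 + 1 = 83. The two rules differ only when L lies in a year before the recorded year of death. In the fourth and fifth rows the OS time stays at L, and only the status changes, from censored to event. That happens only if the cut-off is compared with the imputed date.

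**How often a year-only record would be affected (assumption).** Suppose L is uniform over the year and the gap to death is uniform from 0 to G days. The share crossing into the next year is (G/2)/365, and the mean provable shortening among those is G/3.
- G = 91, about the contact interval: 45.5/365 = 12.5%, and 91/3 = 30 days.
- G = 365, a long gap as for a subject lost to contact: 182.5/365 = 50%, and 365/3 = 122 days.

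These shares apply to year-only records. The number of such records is not in the documents.

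**Effect of a changed status on the hazard ratio.** With d events split equally between arms, SE(log HR) ≈ 2/√d. Moving k extra events into one arm shifts log HR by about k/(d/2).
- No baseline corticosteroids, d = 0.8 × 337 = 269.6: SE = 0.122. For k = 1 the shift is 0.007, or 0.06 SE. For k = 5 it is 0.037, or 0.30 SE.
- All randomized subjects, d = 0.8 × 494 = 395.2: SE = 0.101. For k = 1 the shift is 0.005, or 0.05 SE.

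The values of k are illustrative, and putting all of them in one arm is the worst case. A death that is only misdated keeps its event status and should move the estimate less.

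**The case against.** The strongest objection concerns the cut-off. A reader might infer that the rule will turn deaths after unblinding into events before it. The documents do not support that. The SAP does not give the order of imputation and data cut, and a cut on recorded dates would exclude a death recorded as 2021 before any imputation.

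The route is also narrow. Protocol Table 5.1-3 ends collection of survival status at unblinding. Subjects still in safety follow-up have visits that tend to move the last-alive date past the cut-off, where the two rules agree. A death in the safety window is a serious adverse event, to be reported within 24 hours of awareness (Protocol 6.1 and 6.1.1), so a missing month is unlikely. The route is not closed, because Protocol 3.6 lets the sponsor request survival data off schedule and death is an end-of-study output (SAP 7.13). The effect is therefore possible, but conditional and unlikely.

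A reader might also infer an imbalance between arms, because after unblinding the nivolumab arm has two follow-up visits and placebo subjects at most one. No mechanism is shown. More contact should give later last-alive dates and more complete death dates, and the rule is the same in both arms.

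Protocol 3.6.2 says that "The site staff and representative will consult publicly available sources, such as public health registries and databases", but the stated aim is to update contact information, and sites are separately told to obtain the date of death. The section makes long gaps before a death is found plausible. It is not evidence that year-only dates are common.

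Finally, 1 January is the earliest day of the known year, so the floored rule still tends to shorten OS. That is true, and a cautious convention is a legitimate choice. The difference is that the floored date is possible under the record, while the SAP's date is not.

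**Conclusion.** The point holds as a defect in a stated rule. For a death with a known year and missing month, SAP Section 8 gives a date that the record contradicts whenever the last known alive date is in an earlier year. Each affected time is shortened, by at least 83 days in the 2018/2019 example. This does not depend on how the cut-off is applied.

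The false-event consequence rests on three conditions: a last-alive date on or before 22-Dec-2020, a 2021 death recorded without its month, and a cut-off applied to imputed dates. It does not reach the primary PFS analysis, which uses data cut on 14-Jun-2019 and locked on 09-Aug-2019. It could reach the PFS analysis repeated at the later cut-off.

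The number of affected records is unknown and probably small. The effect on the hazard ratio is expected to be very small, and with conditional power for OS below 1% no conclusion is likely to turn on it. The case for correction is that OS is a primary endpoint that still reports a p-value, the error runs in one direction, and it is easily avoided.

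**What to change.** Replace the month-or-year rule for death dates in SAP Section 8 with:

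*If the month is missing but the year is known, impute 1 January of that year and use the later of this date and the last known date alive; if the year is missing, use the last known date alive. A death whose recorded year or month is after the applicable data cut-off is not an event in that analysis, whatever date is imputed; for OS the subject is censored at the last known date alive on or before the cut-off.*

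This extends the SAP's own missing-day logic and changes nothing when the last-alive date is already in the year of death. It also settles the recorded-or-imputed question for deaths known to fall after the cut-off. The cost is a short change to one section and a small programming change. No new data are needed. Reporting the number of death dates imputed under each rule, by arm, would show whether the issue arose at all.

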Progressive disease ≥ 12 weeks after chemoradiotherapy completion	
 
1. New contrast-enhancing lesion outside of radiation field on decreasing, stable, or increasing doses of corticosteroids.
 
2. Increase by ≥ 25% in the sum of the products of perpendicular diameters between the first postradiotherapy scan, or a subsequent scan with smaller tumor size, and the scan at 12 weeks or later on stable or increasing doses of corticosteroids.
 
3. Clinical deterioration not attributable to concurrent medication or comorbid conditions is sufficient to declare progression on current treatment but not for entry onto a clinical trial for recurrence.
 
4. For patients receiving antiangiogenic therapy, significant increase in T2/FLAIR nonenhancing lesion may also be considered progressive disease. The increased T2/FLAIR must have occurred with the patient on stable or increasing doses of corticosteroids compared with baseline scan or best response after initiation of therapy and not be a result of comorbid events (eg, effects of radiation therapy, demyelination, ischemic injury, infection, seizures, postoperative changes, or other treatment effects).
 

NOTE: Radiologic interpretation guidelines, definitions and tumor measurement instructions will be provided separately in a separate imaging manual. All measurable and nonmeasurable lesions must be assessed using the same techniques as at baseline.

Abbreviations: MRI, magnetic resonance imaging; FLAIR, fluid-attenuated inversion recovery

\* Stable doses of corticosteroids include subjects not on corticosteroids

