4.2 Secondary Endpoint(s)

[figure not shown]
- OS rate at 12 months and 24 months derived Kaplan-Meier curve of OS
- PFS assessed by investigator based on RANO criteria

[figure not shown]

[figure not shown]

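### The rule for partial progression dates in SAP Section 8 has no lower limit, so a month-only progression can be dated before a documented progression-free assessment; year-only dates are left without a stated PFS outcome

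*SAP*

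**What the plan says.** SAP Section 8 (Conventions) treats three kinds of partial date differently.

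- **Progression, day missing.** "If only the day of the month is missing, the 1st of the month will be used to replace the missing day". Then: "In cases where the date of death is present and complete, the imputed progression date will be compared to the date of death", and "The minimum of the imputed progression date and date of death will be considered as the date of progression". There is no comparison with randomization or with the last progression-free assessment.
- **Progression, day and month missing, or no date.** "If the day and month are missing or a date is completely missing, it will be considered as missing".
- **Death, day missing.** The 1st of the month is also used, but with a floor: "The imputed date will be compared to the last known date alive day and the maximum will be considered as the death date". A death with no date but a recorded reason is kept and dated to the last known alive date.
- **Other dates.** "If both the day and the month are missing", 1 July is used.

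The rule feeds the PFS endpoints. The primary one is PFS by BICR in the first 558 randomized subjects (SAP 4.1 and 7.5.2). A secondary one is "PFS assessed by investigator based on RANO criteria" (SAP 4.2). Progression need not coincide with a scan: from 12 weeks after chemoradiotherapy, Protocol Table 5.4.2-1 says "Clinical deterioration not attributable to concurrent medication or comorbid conditions is sufficient to declare progression on current treatment". SAP 7.5.2.2 plans a sensitivity analysis that removes clinical progression from the primary definition, which implies that the primary definition counts it.

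**The concern.** An imputed event date should not contradict what is known about the subject. For death, the section ensures this by not letting the date fall before the subject was last known alive. For progression, the matching fact is that the subject was progression-free at the last assessment, and the rule does not use it.

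For example, a scan on 4 June shows no progression, and a clinical progression is then recorded as June with no day. The rule gives 1 June, three days before the subject was documented progression-free.

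A second gap concerns progressions with only a year or no date. SAP 4.1 defines PFS by the date of first documented progression or death. It censors at subsequent therapy when there is no prior reported progression. A subject whose progression is reported but has no usable date fits neither provision cleanly, so two programmers could code the case differently. If such subjects were censored, the censoring would be informative, because it would follow from an event that had occurred.

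**Working it through.** **1. The plan's own PFS figure.** Inputs from SAP Section 5: HR 0.68, two-sided alpha 0.01, power 90%, 1:1 allocation. Schoenfeld: events = 4(z₀.₉₉₅ + z₀.₉₀)² / (ln HR)² = 4(2.576 + 1.282)² / (−0.3857)² ≈ 400.2, rounded up to 401; Freedman's formula gives 411. Both are within 3% of the stated 404. At 404 events the power is 0.903. These figures are not in dispute.

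**2. Does the check against death do anything?** The 1st of month *m* is never later than a death in month *m* or afterwards. To confirm, every progression day from 1 May 2016 (an assumed start) to 13 June 2019, the day before the PFS cut-off, was paired with a death 0 to 399 days later: 1,139 × 400 = 455,600 pairs. The minimum changed the imputed date in 0 of them. It acts only if the 1st of the recorded progression month is after the death date, that is, if the recorded progression month follows the death month.

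**3. Size of the backward shift.** The shift is the day of the month minus 1. Over those 1,139 days its mean is 14.6 days and its maximum 30.

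**4. When does the imputed date precede a progression-free scan?** Let *g* be the days from that scan to the true progression. The 1st falls before the scan when (day of month − 1) > *g*. In a 30-day month the chance is (29 − *g*)/30. Over the actual calendar:

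| *g* (days) | Share dated before the scan |
|---|---|
| 7 | 73% |
| 14 | 50% |
| 21 | 27% |
| 28 | 5% |
| 30 or more | 0% |

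Scheduled scans are 8 weeks ± 7 days apart, so at least 56 − 14 = 42 days, which exceeds 30. The error therefore cannot occur between two on-schedule scans. It needs a progression-free scan in the same calendar month, hence a clinical progression or an unscheduled scan. Protocol 5.4 allows more frequent scans when medically indicated.

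**5. Share among month-only dates.** Assume *g* is uniform.
- Over 1-56 days, the 30-day-month approximation is Σ(29 − *g*)/30 for *g* = 1 to 28, divided by 56 = (406/30)/56 = 24.2%. Full calendar: 24.4%.
- Over 1-84 days: (406/30)/84 = 16.1%. Full calendar: 16.3%.

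**6. If events were lost to missing dates.** The number is not in the documents. Taking 4, 8 or 20 lost from 404 as illustrations, power is 90.0%, 89.6% or 88.6%.

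**7. What a floor would change.** With the imputed date floored at the day after the last progression-free scan, the share in step 5 is zero by construction. The mean early shift falls from 14.6 to 11.9 days (1-56 days) or 12.8 days (1-84 days). The floor removes impossible dates, not most of the early shift.

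**The case against.** The case for leaving the text alone has several parts.

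- **The check is a data guard.** A reader might infer from step 2 that it can never act. That goes too far: it corrects a record whose progression month follows the death month. This stands.
- **The error is narrow.** It needs a progression-free scan in the same month and cannot arise between on-schedule scans. A randomization floor is rarely needed: radiotherapy takes 6-7 weeks, clinical decline alone does not count until 12 weeks after it, and the shift is at most 30 days. This stands, and limits the size.
- **Events may not be lost.** A reader might infer that year-only progressions are simply not counted. The documents do not establish this. Death from any cause remains a PFS event under SAP 4.1, subject to its censoring rules, and Figure 4.1-1, which presents the primary censoring rules, is not readable here. Nor can any delay be sized by subtracting the planned control medians for PFS and OS, because a difference of two marginal medians is not the time from progression to death.
- **The conventions are optional.** The opening sentence of Section 8 is permissive, but the progression list is introduced as rules that will be applied. This carries little weight.
- **The consequences are small.** BICR progressions would normally carry scan dates, secondary p-values are descriptive (SAP 7.5.4), sensitivity analyses without clinical progression are planned, and the same rule applies to both arms. This stands.

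**Conclusion.** The concern holds as a minor specification defect. Followed exactly, the day-missing rule can place a progression before a documented progression-free assessment, because its only limit is an upper one that has no effect on coherent dates. Under a uniform gap this happens to about 24% (1-56 days) or 16% (1-84 days) of month-only dates. Those shares rest on the uniform assumption and apply only to month-only dates, whose number the documents do not give. For year-only and undated progressions, the supportable statement is that the date is lost and the readable text does not say whether the subject is censored or carried to death.

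The effect falls mainly on investigator-assessed PFS, and on any clinical progression counted in the primary definition. Nothing here changes the 404-event target, the 90% power or the OS analyses.

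**What to change.** In SAP Section 8:

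1. Impute a day-missing progression as the later of (a) the 1st of the recorded month and (b) the day after the last progression-free tumor assessment, or the randomization date if there is none. Keep the existing cap at death.
2. Report the number of imputed and of undated progressions by arm, for BICR and investigator assessment. This shows directly whether the issue matters.
3. Add a sensitivity analysis that keeps year-only or undated progressions as events, dated the day after the last progression-free assessment, or the first day of the recorded year if that is later. Leave the SAP 4.1 censoring rule for subsequent therapy unchanged: forcing an undated progression to fall before the next therapy would turn subjects whom that rule may censor into events.

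The cost is a short SAP edit, a few lines of code and no new data. The drawback is timing. The primary PFS database lock was 09-Aug-2019 and the study was unblinded on 22-Dec-2020, so this would be a derivation change made after unblinding and should be documented as such.
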